This clinical trial will test the methodology and trial retention of one version of a combined therapy (along with comparison control groups). The combination of meditation and exercise will be done sequentially. This methodology is termed (1) Meditation first & then Exercise (Med&Exer). All participants in this exploratory trial will receive the therapeutic intervention, or one of three control options (negative control, meditation only, exercise only) (**Table 1**). We describe below the details of the interventions.

Table 1 – Experimental Conditions	
Experimental Condition	Description
Negative control	In clinic or at home, listen to an audiobook for ~15 minutes followed by 30 minutes of rest (including survey assessments)
Meditation only control	In clinic or at home, 15 minutes of meditation and listen to an audiobook for ~30 minutes (including survey assessments)
Exercise only control	In clinic or at home, listen to an audiobook for ~15 minutes (including survey assessments) then exercise (treadmill) for ~30 minutes
Meditation & then exercise (Med&Exer)	In clinic or at home, 15 min of meditation followed by 30 min of exercise (treadmill) plus survey assessments

Exercise in this exploratory study will consist of 30 minutes of moderate-intensity treadmill walking (starting at 3.5 mph and adjusted up or down to reflect moderate intensity for each individual participant) in the Rangos Human Testing Facility (Fisher Hall) on a treadmill with auto-shut off and integrated heart rate monitor (Polar H1 Heart Rate Sensor) on day 2 (first day of intervention), day 9, day 16, and day 23. During the other intervention days (day 3-6, 10-13, 23-27) participants will have the option of completing trials at Duquesne or “at home.” At home is defined as a participant using a personal treadmill or going to a community fitness center (e.g. YMCA). This “at home” component is designed to reduce the extra burden for patients who would otherwise have to travel to Duquesne for 22 total sessions (20 days of intervention plus intake and outtake sessions). Exercise will

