Assessments in this exploratory trial are designed to evaluate four elements of the trial: (1) Pain and Disability, (2) Meditation, (3) Anxiety and Stress, and (4) Fitness and General Health and. Although these elements are not mutually exclusive and multiple survey tools overlap, we describe these elements as individual groups of assessments below for ease of interpretation. General assessment includes demographic information (gender, age, race/ethnicity, and education level) and handedness. The primary outcome of this trial is a reduction in disability as measured by the RMDQ (see below). See Appendix 1 – Instruments for all surveys and questionnaires.

Protocol Pain and Disability

There are multiple assessments for experimental measurement of pain. First, we will use the Roland-Morris Disability Questionnaire, which provide a qualitative analysis of the disability that is associated with an individual's chronic low back pain. This is our primary outcome for the trial. We hypothesize that exercise, meditation, and combined exercise/meditation will decrease disability in patients. Second, we will use standard visual analog scoring of instantaneous back pain for participants before and after exercise (or meditation in the "meditation only" control group or audio book in the negative control group) during each day of the trial. These scales will be included in the subject online diary (Qualtrics Survey Platform) for participants completing "at home" trials.

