Title Page:

Statistical Analysis Plan

Combined exercise and meditation as a treatment for patients with chronic back pain

NCT number not available

12/21/17

Statistical Analysis Plan
Combined exercise and meditation as a treatment for patients with chronic back pain

This is a single-blind, single center randomized clinical trial comparing a treatment group (MedExT) versus a control group. The current analysis plan is specific to this study for reporting and publication purposes but is part of a larger study. The primary outcome of this study is to compare the post Roland-Morris Disability Questionnaire scores between the two independent groups. This will be achieved by comparing the mean post disability score for the MedExT group to the mean post disability score for the control group using a two-sample t-test (or the Mann-Whitney-Wilcoxon rank sum test if normality does not hold) in which a one-sided p-value < 0.05 will be considered a significant improvement in the MedExT group.

Three secondary treatment responses will be studied. The first will test whether the MedExT group will significantly increase mean scores on the Freiburg Mindfulness Inventory as determined by a two-sample t-test or the Rank Sum test given distributional properties of the data ($P < 0.05$). The second will explore whether the MedExT treatment will significantly influence a mean change in responses on the three psychological inventories administered; the Fear Avoidance Beliefs Questionnaire, the STAI state anxiety inventory and the STAI state trait inventory, $p < 0.02$. The third outcome measured will study mean response changes in the series of 14 Quantitative Sensory Tests measured at baseline and at the completion of the 4-week intervention period. Significant mean pre/post differences between groups will be identified using the two-sample t-test or the Rank Sum test where appropriate adjusting the significance level to 0.005. Additionally two pain outcome measures will be repeatedly observed throughout the study taken at baseline and on each intervention day. These measures are the VAS pain intensity score and the VAS pain unpleasantness. A repeated measures multivariate analysis of variance (MANOVA) procedure will be used to determine if the vector of timed responses is significantly different between the two study groups.

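### As written, the combined arm's daily back-pain VAS starts after that day's meditation, as in no control arm, and the SAP does not say which reading it analyses

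*Protocol*

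**What the plan says.** Protocol section 4 (Protocol Pain and Disability) sets the daily back-pain measure as "visual analog scoring of instantaneous back pain for participants before and after exercise". The parenthesis that follows gives the substitute for the arms that do not exercise: "or meditation in the 'meditation only' control group or audio book in the negative control group) during each day of the trial". The anchor is therefore one component of the session, and it depends on the arm.

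Table 1 in section 3 gives the session content:

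- Combined arm (Med&Exer, called MedExT in the SAP): "15 min of meditation followed by 30 min of exercise (treadmill) plus survey assessments".
- Exercise only: "listen to an audiobook for ~15 minutes (including survey assessments) then exercise (treadmill) for ~30 minutes".
- Meditation only: "15 minutes of meditation and listen to an audiobook for ~30 minutes", with surveys counted inside that time.
- Negative control: about 15 minutes of audiobook, then 30 minutes of rest that includes the surveys.

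State anxiety is handled differently. Section 4 (Assessment – Anxiety) has it reported before and after each session, with the same wording for every arm.

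The SAP's paragraph on secondary responses says that VAS intensity and unpleasantness are "repeatedly observed throughout the study taken at baseline and on each intervention day". A repeated-measures MANOVA then tests whether the vector of responses differs between MedExT and a control group. The SAP does not name that control arm and does not say which of the day's two readings enters the vector.

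**The concern.** The VAS analysis is the SAP's only repeated measure of back pain over the four weeks. A reader will take a group difference in it as evidence that pain changed over the course of treatment. That reading needs a daily score that means the same thing in both groups and does not already contain part of that day's treatment.

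Under the protocol's wording the combined arm has no such score. Its first reading of the day comes after meditation and its second after meditation and walking. The Day 1 baseline precedes every intervention session. An immediate effect that fades between sessions would therefore be absent at baseline, appear at the first session and recur at each one. In the MANOVA this would look like a treatment effect over time, although pain at the start of each session had not changed.

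**Working it through.** The documents give no VAS standard deviation, effect size or sample size, so there is no planned figure to reproduce. The check is a reading of the session order, followed by simple bookkeeping.

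**Step 1. What has happened before each reading.** This applies the section 4 anchors to the Table 1 order. Minutes are approximate and inferred.

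| Arm | 'Before' reading | 'After' reading | Before-after change covers |
|---|---|---|---|
| Combined | after meditation (about 15) | after meditation and exercise (about 45) | exercise |
| Exercise only | after or within the audiobook (up to about 15) | after exercise (about 45) | exercise |
| Meditation only | before meditation (about 0, if meditation comes first) | after meditation (about 15) | meditation |
| Negative control | before audiobook (about 0) | after audiobook (about 15, or later if taken during rest) | audiobook |

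In clock time there are two patterns: about 15 and 45 in the two walking arms, and about 0 and 15 in the other two. Combined and negative control differ by 15 − 0 = 15 minutes at 'before' and 45 − 15 = 30 minutes at 'after'.

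**Step 2. What each between-group difference contains.** Let C be the difference between groups in pain at the start of a session, which is the four-week effect of interest. Let m, e and a be the same-session effects of meditation, exercise and audiobook. Assume that these effects add and do not fade within the session. For combined minus control:

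| Control arm | 'Before' score | 'After' score | Before-after change |
|---|---|---|---|
| Negative control | C + m | C + m + e − a | e − a |
| Meditation only | C + m | C + m + e − m = C + e | e − m |
| Exercise only | C + m − a | C + m + e − (a + e) = C + m − a | e − e = 0 |

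No cell isolates C. The term m enters the 'before' contrast whichever arm the SAP means. The exercise-only row takes that arm's 'before' score at the end of the audiobook; if it is taken earlier, only part of a applies. The change score never measures m + e in the combined arm.

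**Step 3. How many values are exposed.** There are 20 intervention sessions. With one reading per day the vector has 1 + 20 = 21 values per scale; with both it has 1 + 40 = 41. Every value except baseline is exposed.

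**Step 4. Illustration of size, all inputs assumed.** Set C = 0 and compare a single day's 'before' score, combined versus negative control, at two-sided 0.05 with n per arm. The chance of a significant difference is approximately Φ(m / (SD·√(2/n)) − 1.96).

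- With n = 20 and SD = 2.0, SD·√(2/n) = 2.0 × 0.316 = 0.632.
- m = 0.5: Φ(0.79 − 1.96) = 12%.
- m = 1.0: Φ(1.58 − 1.96) = 35%.
- m = 1.5: Φ(2.37 − 1.96) = 66%.
- Over n from 15 to 40 and SD from 1.5 to 2.5, the ranges are 8% to 32%, 19% to 85% and 38% to 99%.

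The nominal rate is 5%. These figures describe a single-day comparison and not the planned MANOVA. They show only that a modest immediate effect could matter.

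**The case against.** The best reply is that 'exercise' in section 4 may be shorthand for the whole session. The protocol runs exercise and meditation together elsewhere, Table 1 does not place the surveys within the combined session, and staff may have scored everyone at the start. The survey appendix and online diary are not in the text reviewed, and either could settle the timing. This stands as a limit on confidence. It does not remove the point, because nothing in the available text places the combined arm's first VAS before meditation, and the anxiety paragraph shows that the protocol can state a whole-session anchor.

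The minutes are also softer than the table suggests. Survey time sits inside the audiobook or rest period in the three control arms, and the order in meditation only is implied, not stated. The argument in step 2 needs the order of events, not exact minutes.

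Anchoring a before-after score to an arm's main activity is a legitimate way to measure that activity's immediate effect. That is fair for the within-session change in the single-component arms. It does not provide a score for the four-week comparison, and in the combined arm it leaves meditation out.

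Four stronger readings are tempting, and the documents do not support them:

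- A reader might infer that every arm is scored at a different time. There are two clock patterns, and exercise only shares the combined arm's times approximately.
- A reader might infer that the SAP uses one score per day. It leaves open the before score, the after score or both.
- A reader might take the negative control as the SAP's comparator. The SAP does not name the arm; against exercise only the clock gap largely disappears and the meditation term remains.
- A reader might conclude that the trial's main result is compromised. The primary outcome is the RMDQ, and the sensory tests are taken on day 29, 48 hours after the last session. Neither depends on the daily VAS.

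**Conclusion.** The point holds as a gap in measurement and analysis that is cheap to close. On the literal wording, the combined arm alone is first scored after that day's meditation, its change score omits meditation, and the SAP does not say which reading it compares. Same-session effects can therefore be taken for a four-week effect.

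All 20 intervention days are exposed on both VAS scales. The size is unknown: the bias in the 'before' contrast equals m against negative control or meditation only, and the documents give no value for m. The percentages in the working are illustrations under assumed inputs.

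The conclusion rests on reading 'before exercise' literally and on the Table 1 order. Confidence is medium for that reason. The consequence is confined to the daily VAS analysis, which the SAP lists after the primary outcome and the three secondary responses and for which it states no significance level.

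**What to change.** In protocol section 4, state that the VAS is taken in all four arms at the start of the session, before any meditation, audiobook or exercise, and again at the end of the full session. This matches the approach already used for state anxiety.

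In the SAP, name the session-start score as the daily value for the repeated-measures comparison, say which arm is the control group, and report end minus start separately as the immediate session effect. In the notation above, the start-score contrast is then C in every comparison, and the combined arm's change becomes m + e.

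If the diary already scores at session start, only the wording needs correcting. If sessions have already been recorded under the present wording, the SAP should state when the readings were actually taken, because a timing mismatch in collected scores cannot be removed by analysis.

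The cost is a sentence in the protocol, a short addition to the SAP and moved diary prompts, with no extra readings or visits. The one loss is the mid-session reading that isolates exercise within the combined arm.

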All participants in the meditation groups will complete the Freiburg Mindfulness Inventory (FMI) at the beginning of their first day of exercise/meditation and on the last day of the trial. The FMI is a 30-item tool that assesses an individual's experience with meditation and mindfulness. For this feasibility study, data from the FMI will be particularly useful in evaluating whether there were any changes in mindfulness that developed during the trial. Failure to increase mindfulness during the trial might be a sign that a patient failed to "buy in" to the meditation intervention. We will also evaluate the likelihood of a patient to continue to meditate (or exercise) using a qualitative exit survey given on day 29. There are no safety concerns associated with the FMI or custom exit survey.

Assessment – Anxiety

To account for changes in anxiety during the current exploratory trial, we will use the State-Trait-Anxiety Inventory (STAI) form Y to evaluate state anxiety and the Fear-Avoidance Beliefs Questionnaire (FABQ) to evaluate fear avoidance behavior. Subjects will report their state anxiety (using a survey) before and after each trial. FABQ will be evaluated on day 1 and day 29. There are no serious safety concerns associated with this survey.

Assessment - Exercise

As described above, we will be using multiple assessment tools to evaluate physical fitness and exercise in this trial. General fitness will be determined by the International Physical Activity Questionnaire – Short Form (IPAQ-short) and a clearance of physical readiness for exercise will be determined by the AHA/ACSM Health/Fitness Facility Pre-participation Screening Questionnaire. Exercise exertion will be measured daily through active heart rate monitoring during exercise and the Borg Rate of Perceived Exertion (Borg RPE)⁸. Finally, throughout the 4 week trial, participants will be asked to wear wrist-based health activity monitors. These watches monitor and record activity and other factors. There are no serious safety concerns associated with these surveys or monitoring methods.

5. Sample selection

Adults with chronic low back pain who are otherwise healthy will be recruited for participation in this study. The AHA screening questionnaire will be administered during the screening process to determine whether potential subjects meet the inclusion/exclusion criteria.

Eligibility Criteria:

Inclusion criteria

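### The SAP tests the Freiburg Mindfulness Inventory (FMI) between MedExT and an unnamed control, but the protocol schedules the FMI in only one of the three control arms

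*Protocol*

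**What the plan says.** Protocol section 3 (Intervention Sessions, with Table 1) gives participants the combined intervention or "one of three control options (negative control, meditation only, exercise only"), which makes four arms. Two of these meditate: meditation only, and meditation followed by exercise.

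Protocol section 4 (Assessment - Meditation and Mindfulness) assigns the questionnaire: "All participants in the meditation groups will complete the Freiburg Mindfulness Inventory (FMI) at the beginning of their first day of exercise/meditation". It places the second administration on the trial's last day. Section 3 ties the first FMI to the moment just before a participant's first meditation, and puts the second on Day 27. It also describes a 45-minute training session on Day 1, which covers mindfulness and meditation in the meditation groups and stress management in the other two arms.

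The SAP describes the trial as "comparing a treatment group (MedExT) versus a control group" and does not say which control this is. Its first secondary analysis reads: "The first will test whether the MedExT group will significantly increase mean scores on the Freiburg Mindfulness Inventory as determined by a two-sample t-test", with the rank sum test as the alternative.

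**The concern.** A two-sample test needs scores in both groups. The protocol plans FMI scores only where participants meditate, while the SAP's wording allows a control group that does not. Followed literally, the two documents can leave the first-listed secondary analysis with no data on one side.

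The one single-arm control with scheduled scores also meditates. That comparison holds meditation constant and varies exercise, whereas section 3 introduces the FMI as a way to evaluate the effect of meditation. A null result there would not show whether the combined treatment raises mindfulness over no meditation.

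Two timing matters bear on any repair: whether the first FMI is a true baseline, and on which day the last one falls. A pre-training score that was not collected cannot be obtained later.

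**Working it through.** The documents give no sample size, effect size, standard deviation or allocation ratio for the FMI, so there is no planned figure to reproduce. The check is a count of arms and a comparison of texts.

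**Arms with a scheduled FMI.** Arms in Table 1: negative control, meditation only, exercise only, and meditation then exercise = 4. Arms that section 4 assigns the FMI: meditation only, and meditation then exercise = 2. That is 2 of 4 arms overall and 1 of 3 controls.

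**What the SAP's test becomes under each reading of the control group.**

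| Control group | Scheduled comparator FMI scores | What the test can address |
|---|---|---|
| Negative control | None | Cannot be run |
| Exercise only | None | Cannot be run |
| Meditation only | Yes | Added exercise, with meditation in both groups |
| All three pooled | From the meditation-only arm alone | Added exercise, as in the row above |

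So 2 of the 3 single-arm readings have no comparator data. Under pooling, one control arm of three supplies scores. That would be about 1/3 of control participants if allocation were equal, which is an assumption. No reading gives a comparison with people who do not meditate.

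**Is the first FMI a baseline?** The training is on Day 1. Intervention begins "on day 2 (first day of intervention), day 9, day 16, and day 23", so the first FMI falls on Day 2, after the meditation groups have had mindfulness training. Write the final score as F, the Day 2 score as B2 and the pre-training score as B1. The total change is F − B1 = (F − B2) + (B2 − B1). A change score from Day 2 uses only F − B2 and leaves out B2 − B1, the part already present after training. Against a non-meditating control, a change-score analysis would therefore omit any training gain. A comparison of F alone omits nothing. The documents give no size for B2 − B1, so none is claimed. The SAP does not settle which variable is meant. It compares post scores for the primary outcome, and for other secondary measures it asks whether treatment will "significantly influence a mean change in responses on the three psychological inventories administered". For the FMI it speaks only of increasing mean scores.

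**Which day is the last FMI?** Section 3 says Day 27. Section 4 says the last day of the trial, and section 3 also says that each trial lasts 29 days. Pain testing on Day 29 is placed 48 hours after the last intervention, so the last intervention day is 29 − 2 = Day 27. The two statements differ by 2 days.

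The choice has practical consequences. Day 27 is not a required campus day: "During the other intervention days (day 3-6, 10-13, 23-27) participants will have the option of completing trials at Duquesne". Day 29 is the exit session, which section 6 limits to participants who complete enough of the intervention sessions (80%).

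**The case against.** The strongest defence is that the protocol never says the FMI is confined to the meditation groups. Section 8 promises means and standard deviations for all quantitative measures in all groups. Table 1 mentions survey assessments in all four conditions, in clinic or at home. The SAP is dated 12/21/17, after the protocol of 10/24/17, and describes itself as part of a larger study, so collection may have been widened.

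Part of this stands. The restriction is an inference from the arms that section 4 names and from the absence of any other schedule. It remains the natural reading. Section 8 is about reporting and does not schedule collection. Table 1 does not name the FMI. The timing in section 3, before the first meditation, has no meaning in arms that do not meditate. The SAP gives no FMI schedule. If practice has changed, neither document says so.

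A reader might also infer more than the documents support:

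- That the test is impossible under every reading. It is not, because a meditation-only control supplies scores.
- That the Day 1 training biases the FMI comparison. This applies only if a change or baseline-adjusted analysis from Day 2 is used, and the SAP does not commit to one.
- That the test is lost once controls have enrolled without a first FMI. A comparison of final scores between randomised groups needs no baseline.
- That an off-campus final FMI would need a new collection system. The online diary already carries pain scales (section 4) and adverse-event reports (section 9).

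**Conclusion.** The point holds as a mismatch between the protocol's collection schedule and the SAP's test. As written, the first secondary analysis either has no scheduled comparator data (negative control or exercise only) or can only address added exercise (meditation only or pooled controls). In no case can it show that the combined treatment raises mindfulness over no meditation.

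The damage is limited. The primary disability comparison does not use the FMI. The scheduled scores still serve the section 4 check on whether participants took to the meditation. A within-arm change cannot stand in for the between-group test, because it mixes treatment with time, expectancy and repeat testing.

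The conclusion assumes that MedExT is the protocol's meditation-then-exercise arm, which is inferred from the names, and that the FMI is collected only where the protocol schedules it. A reader might conclude that comparator scores will be absent in the actual data. The documents support only the statement that none are scheduled in two of the three control arms.

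**What to change.** 1. In the SAP, name the arm that forms the control group. To test mindfulness against no meditation, it must be a non-meditating arm.
2. In protocol sections 3 and 4, have every participant in the compared arms complete the FMI on Day 1 with the intake surveys, before the training session, and again on one stated final day. Reconcile Day 27 with Day 29. Whichever is chosen, collect the FMI whether or not the participant meets the 80% rule for the exit session. If the day falls off campus, the existing online diary can carry it.
3. In the SAP, analyse the final FMI score adjusted for the pre-training score.
4. If enrolled controls have no baseline FMI but can still give a final score, compare final scores. If no comparator FMI can be obtained, drop the between-group test and report within-arm change descriptively.

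The cost is one 30-item questionnaire, twice, in the added arm, and a move of the first FMI from Day 2 to Day 1 in the meditation arms. Intake surveys are already completed on Day 1, so no visit is added there. Participants who have stopped sessions need some follow-up for the final form. Controls will see mindfulness items, which is a minor priming risk.

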Activity		-15 min meditation -30 min exercise (In clinic)	-15 min meditation -30 min exercise	Rest	Rest				
Day		23	24	25	26	27	28	29	
Activity		-15 min meditation -30 min exercise (In clinic)	-15 min meditation -30 min exercise	Rest	Pain Assess and Exit Survey (In clinic)				

while the subjects complete these forms. Basic health information obtained from the subject will assess whether the subject has been diagnosed with any cardiac, respiratory, neurological or musculoskeletal disorder, chronic pain or currently has acute pain (AHA health questionnaire). Subjects who report any of the above medical diagnoses or pain (with the exception of chronic low back pain) during screening will be excused from participation in the study. Subjects who cannot walk independently without a device will be excused from participation as well. Any identifying information used to determine eligibility, including the checklist of inclusion/exclusion criteria and the health questionnaires, will be destroyed.

Each trial is designed to last 29 days including an intake session and a post-meditation/exercise pain testing session. Pain testing is performed during the intake session (baseline) and on day 29 (48 hours after the last intervention). See **Figure 1** for illustrative time-line of individual trials for individuals assigned to the meditation then exercise group. Analogous time-lines will be used for exercise only subjects (30 minutes of exercise each day and 15 minutes of audiobook), meditation only subjects (15 minutes of meditation each day and 30 minutes of audiobook) or negative control subjects (15 minutes of audio book followed by 30 minutes of rest each day).

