Compensation for participation in this study is based on the number of sessions completed. Compensation for the intake session and each completed intervention session is \$4.50 and compensation for the Exit Session is \$100. Therefore, if a participant completes this project in its entirety (intake session, 20 intervention sessions, and the Exit session), they will receive \$200. Only participants who complete at least 80% of all intervention sessions (greater than 16 of 20 sessions) and the intake session, will be invited to complete the Exit Session. If the subject chooses to withdraw before completing at least 80% of the intervention sessions, they will receive partial compensation for the sessions that they have completed.

As part of this study, we are also interested in identifying barriers to participant interest and persistent. To identify these barriers, we will utilize an anonymous online survey of participants who drop out of the study. If a participant consents to the Duquesne study but later drops out of the study, they will be directly given a URL for a survey.

7. Informed consent procedures for exercise/meditation study

As noted above, initial consent is obtained through the University of Pittsburgh Department of Physical Meditation and Rehabilitation Research Registry (PMR3) (Pitt IRB # PRO12030122). This consent is obtained by UPMC/Pitt Physician [name] (co-I), and his partners, Drs. [name], [name], and [name] (see *Support Letter*) along with Physical Medicine and Rehabilitation Clinical Research Coordinator [name], MS. Backup recruitment efforts will occur in collaboration with the CTSI (see *Support Letter*) using the Pitt + Me registry. IRB approved consent is provided when patients are entered into the Pitt + Me registry.

Subsequent consent for the exercise/meditation study here at Duquesne occurs as follows:

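### Only participants above a self-contradictory adherence cut-off are invited to the Day 29 visit, so the outcomes measured there are not collected from enrolled participants below it

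*Protocol*

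**What the plan says.** The compensation paragraph of Protocol Section 6 sets the rule: "Only participants who complete at least 80% of all intervention sessions (greater than 16 of 20 sessions) and the intake session, will be invited" to the Exit Session. It goes on: "If the subject chooses to withdraw before completing at least 80% of the intervention sessions, they will receive partial compensation" for the sessions they did complete. For those who leave, "we will utilize an anonymous online survey of participants who drop out of the study".

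The Exit Session is the Day 29 visit. The Figure 1 time-line in Protocol Section 3 ends on Day 29 with an in-clinic pain assessment and exit survey, and Sections 3 and 6 both count one intake session, 20 intervention sessions and one final session.

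Measures expressly placed on Day 29:
- QST: "Pain testing is performed during the intake session (baseline) and on day 29 (48 hours after the last intervention"), repeated in Section 4.
- Fear avoidance: "FABQ will be evaluated on day 1 and day 29".
- Acceptance: Section 4 evaluates the "likelihood of a patient to continue to meditate (or exercise) using a qualitative exit survey given on day 29".

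Measures with no written post-intervention day:
- The RMDQ. Section 4 says "The primary outcome of this trial is a reduction in disability as measured by the RMDQ" but gives no day, and the SAP speaks only of a post score.
- The STAI trait scale, which the SAP lists for testing.

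Measures the rule does not touch: the daily back-pain VAS, and state anxiety ("Subjects will report their state anxiety (using a survey) before and after each trial").

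The SAP compares two groups by t-test or rank-sum test, with a one-sided 0.05 criterion for the primary outcome. It names no analysis set and no method for missing data. Protocol Section 8 plans to report withdrawal and adherence as percentages.

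**The concern.** The number of sessions completed is known only after randomisation and may depend on the assigned arm and on how the participant is doing. Using it to decide who is measured means that the groups compared on Day 29 are no longer the groups that were randomised. The rule acts at collection, so no later analysis can recover the data.

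The feasibility aim is touched even if the RMDQ is set aside. Protocol Section 2 lists treatment acceptance among its feasibility indicators, yet the survey on willingness to continue would be answered only by people who had already met the cut-off. Section 8 also intends the means, standard deviations and effect sizes to inform a larger trial. For Day 29 measures, those estimates would describe adherers only.

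Separately, the two statements of the cut-off cannot both be applied to a participant with exactly 16 sessions.

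**Working it through.** **1. The plan's own figure.** 0.80 × 20 = 16, so the percentage admits 16 or more. The parenthesis admits 17 or more, and 17/20 = 85%. The two do not agree.

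**2. How many participants the wording moves.** This is P(exactly 16 of 20). The documents give no session-completion rate, so the rate is assumed.

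| Assumed rate per session | Pass at ≥16 | Pass at ≥17 | Exactly 16 |
|---|---|---|---|
| 80% | 63.0% | 41.1% | 21.8% |
| 85% | 83.0% | 64.8% | 18.2% |
| 90% | 95.7% | 86.7% | 9.0% |
| 95% | 99.7% | 98.4% | 1.3% |

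These are binomial and treat sessions as independent. If attendance clusters within person (beta-binomial, intra-person correlation 0.1 to 0.3), the share at exactly 16 is 2.1% to 11.8%.

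**3. What selection could do to a between-arm test (illustration only).** The documents give no sample size, SD or completion rate. Assumptions: no true effect; a share p passes the cut-off; propensity to complete is a latent normal variable with correlation r to a good outcome; 20 to 40 randomised per arm; one-sided 5% test; control completion 90%.

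Formulas: c = z(1−p); λ = φ(c)/p; completer mean shift = rλ; completer variance = 1 − r²λ(λ−c); bias = difference in shift between arms; error = 1 − Φ(1.645 − bias/SE), with SE from n × p per arm.

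Worked case, r = 0.3, MedExT 70%:
- MedExT: λ = 0.3477/0.70 = 0.497, shift = 0.3 × 0.497 = 0.149 SD, variance 0.954.
- Control: λ = 0.1755/0.90 = 0.195, shift = 0.3 × 0.195 = 0.0585 SD, variance 0.974.
- Bias = 0.149 − 0.0585 = 0.091 SD.
- n = 20: SE = √(0.954/14 + 0.974/18) = 0.350, error 8.3%. n = 40: SE = 0.247, error 10.0%.

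That counts all non-completion. The rule's own part is smaller. Let f be the share of those below the cut-off, in each arm, who are still enrolled and would attend. Without the rule they join the observed group, with mean shift −rφ(c)/(1−p).

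| Scenario | Bias with rule (SD) | Error with rule | Bias without rule, f = 0.5 (SD) | Error without rule, f = 0.5 |
|---|---|---|---|---|
| r = 0.2, MedExT 80% | 0.031 | 6.0%–6.5% | 0.013 | 5.4%–5.6% |
| r = 0.3, MedExT 70% | 0.091 | 8.3%–10.0% | 0.034 | 6.1%–6.7% |
| r = 0.5, MedExT 50% | 0.301 | 20.4%–31.3% | 0.087 | 8.2%–9.9% |

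At f = 0 the rule adds nothing. With completion rates swapped between arms, the bias has the same size and opposite sign, and the error falls below 5% (2.2%–2.9% in the middle scenario). With equal completion and equal r, the bias is 0 and the error 5%.

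**4. Exit survey.** Overstatement of willingness = share below the cut-off × difference in willingness. If 10% to 50% are below and are 0 to 30 percentage points less willing (all assumed), the overstatement is 0 to 0.50 × 30 = 15 points at most.

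**The case against.** The strongest reply is that the rule may do little. Participants may withdraw at any time, and that loss would occur without it. Its own contribution is confined to people still enrolled but under-adherent, and the documents give no means of sizing that group. The large figures above need a 40-point completion gap that nothing in the protocol supports; all arms have sessions of about 45 minutes and one required campus visit a week. The trial is exploratory, withdrawal and adherence are reported, and drop-outs are asked for their reasons. The $100 exit payment may also act as an adherence incentive, and adherence is itself a feasibility result. All of this stands, and it lowers the severity.

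It does not remove the rule. Percentages of withdrawal and adherence do not supply missing scores, and an anonymous survey cannot be linked to a participant's outcomes.

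Three stronger readings are tempting but unsupported:
- That the primary outcome is certainly lost below the cut-off. Day 29 is the only visit after the intervention, so this is likely, but no day is written for the post RMDQ.
- That the rule favours MedExT. The direction depends on which arm loses more participants and which participants those are, and the documents do not say.
- That the SAP prescribes a completer analysis. It names no analysis set; restriction to those above the cut-off would be a consequence of what is collected.

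**Conclusion.** The cut-off is wrong as written: 16 and 17 cannot both be the threshold. Beyond that, the rule limits QST, FABQ and the exit survey to participants selected after randomisation, and probably the post RMDQ and STAI trait score as well. The direction and size of any bias are unknown, and it may be nil. The error rates above show what selection could do under assumed correlations, completion rates and sample sizes; they do not estimate what will happen in this trial.

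This is a cheap improvement, not a condition for the trial to go ahead. It should be made before Day 29 data are collected. The conflicting days for the Freiburg Mindfulness Inventory and the SAP's unspecified control group would exist without this rule and are separate points.

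**What to change.** 1. **Protocol Section 6.** Invite every randomised participant to the Day 29 assessment, whatever the number of sessions completed, unless they withdraw from follow-up. Offer the questionnaires through the existing Qualtrics platform to those who cannot attend.
2. **Payment.** Decide the exit payment separately from the invitation, so that any adherence incentive can be kept. Reconcile the 16 and 17 wordings wherever a cut-off remains, whether for payment or for a supplementary completer set.
3. **Protocol Section 4.** State the day of the post RMDQ.
4. **SAP.** Make the primary set all randomised participants with Day 29 data, grouped as randomised. Add a sensitivity analysis for missing data and keep completers as supplementary only. Report Day 29 completion by arm, with those below the cut-off split into withdrawn and still enrolled, so that the rule's share of the loss can be seen.

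**Cost.** A protocol and SAP amendment, new consent wording, and for each extra attendee one blinded QST visit and up to $100. With 20 to 40 per arm and 10% to 50% below the cut-off (assumed), the maximum is 20 × 0.10 = 2 to 40 × 0.50 = 20 extra attendees, or $200 to $2,000 per arm. If a quarter of them attend, it is $50 to $500. If the full exit payment no longer depended on sessions completed, adherence might change; deciding payment separately guards against that.
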